5.10.5 Physical Examination

Data collected on each physical examination body system eCRF page will be listed but not summarized. Abnormal findings will be flagged (abnormal not clinically significant/abnormal clinically significant).

Any abnormal, clinically significant physical examination results recorded as MH or AEs, will be summarized accordingly in the AE or MH summary tables.

5.10.6 Additional Safety Assessments

5.10.6.1 Gallbladder Examination

Gallbladder imaging results details (location of gallstones, gallbladder sludge, or other findings) will be listed for each patient at each assessed visit.

[figure not shown]
5.11 Pharmacokinetic Analyses

All individual plasma octreotide concentration data for CAM2029 will be listed. Individual concentration-time profiles will be displayed graphically by patient on the linear and semi-log view.

The PK analysis set will be used for all summaries of plasma octreotide concentrations in this section unless specified otherwise.

[figure not shown]
Descriptive statistics (n, m [number of non-zero concentrations], arithmetic mean, coefficient of variation percentage mean, standard deviation, median, geometric mean, coefficient of variation percentage geo-mean, minimum and maximum and 95% CIs of the mean) for octreotide concentration will be presented at each scheduled time point by CAM2029 dose regime. Concentration values below the limit of quantification (BLOQ) will be treated as 0 for the computation of descriptive statistics.

Summary concentration-time profiles will be displayed graphically.

Possible derivation and analyses of PK parameters, Population PK analyses, PK/efficacy analyses and PK/safety analyses including data from this trial is outside the scope of this statistical analysis plan and will be performed and reported separately, if applicable.

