4.1.2 Double-Blind Treatment Period

Eligible patients will receive their first dose of IMP (CAM2029 or placebo) on Day 1. Patients will be treated with IMP as an SC injection every week for a total of 52 weeks. Patients will be

encouraged to perform self- or partner-administration at home, which is allowed after appropriate training (see [Section 6.2.2](#)).

Following Day 1, there will be at least 6 visits during the 52-week Double-Blind Treatment Period (Weeks 5, 13, 21, 25, 39 and 53) for assessment of efficacy, PK, PD and safety. At Week 2, trial personnel will contact the patients by phone to assess any concomitant medication and AEs. Additional visits may be necessary for training of self- or partner-administration of IMP or for IMP administration by trial personnel if self- or partner-administration is not possible. Where applicable, patients will be offered the possibility to complete trial visits at home. In such cases a nurse will come to the patient's home.

Patients who discontinue IMP treatment during the Double-Blind Treatment Period will continue to be followed in the trial and complete all the assessments up to Week 53 (see [Section 6.10.1](#)). A PK sample and an immunogenicity sample should be collected at least 5 weeks after the last dose of IMP.

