6.2.2 Self-Administration

Self- or partner-administration of the IMP will be encouraged after appropriate training, including at least 1 self- or partner-administration under the supervision of trial personnel who has been adequately trained. A “partner” may be the patient’s spouse, parent, child, or sibling etc. or any other person that the patient trusts to administer the injection. The first self- or partner-administration should preferably be performed on Day 1. Trained trial personnel will document that the patient or partner understands the administration process, performs the injection correctly and administers a full dose (a checklist of the feasibility of self- or partner-administration will be provided separately). If the patients or their partners are considered competent to administer IMP, they may continue with the self- or partner-administration at home, starting from Week 2. If the partner who is administering IMP is replaced, the new partner must undergo appropriate training, as described above.

The Investigator or designated personnel will dispense an appropriate number of IMP packages for home administrations. The patients will use a patient diary to record date(s), and exact

time(s) of administration, the injection site, and who performed the injection. The trial personnel will document the administration dates and confirm whether the full dose was administered. Detailed instructions will be provided separately.

Patients will be instructed not to make up missed doses. A missed dose is defined as an event when the planned IMP dose is not taken ± 2 days from the scheduled day of the dosing. In case of missed dose(s), the patient will continue treatment with the next scheduled dose as planned regardless of how many doses they miss. The site personnel should follow up with the patient to find out the reason for missing dose(s).

Patients will be asked to return any used and unused pens and packaging for assessment of accountability (see [Section 6.6.1](#)). It is important that patients contact the Investigator/trial personnel if they experience any AE/SAE or have any concerns, or if there are any problems with the medication (e.g., if there is something wrong with the pre-filled pen), during the period of IMP administration at home.

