6.10 Discontinuation and Withdrawal Criteria

6.10.1 Discontinuation of Treatment

Patients may voluntarily discontinue from treatment for any reason at any time. If a patient decides to discontinue from treatment, the Investigator must make every effort to determine the primary reason for this decision. The reason for discontinuation should be recorded in the patient's chart and on the appropriate eCRF pages.

Patients who discontinue IMP treatment during the Double-Blind Treatment Period should NOT be considered withdrawn from the trial. Every effort will be made to keep patients who discontinue IMP treatment in the trial. They should return for the assessments indicated in Table 3, up to Week 53. A PK sample and an immunogenicity sample should be collected at least 5 weeks after the last dose of IMP.

If the patients fail to return for these assessments for unknown reasons, every effort (e.g., telephone, email, letter) should be made to contact them. Patients who discontinue IMP treatment during the Extension Period should be asked to complete an End-of-Treatment Visit as soon as possible after the last dose of IMP, and a Safety Follow-Up Visit at least 5 weeks after last dose of IMP.

The Investigator should discontinue a patient's IMP treatment if he/she believes that continuation would be detrimental to the patient's well-being or if the patient experiences an intercurrent illness that compromises the patient's ability to fulfil protocol requirements. The Investigator should contact the Medical Monitor before a patient is discontinued from IMP treatment.

IMP treatment must be discontinued under the following circumstances:

- Development of decreased kidney function as defined by $\text{eGFR} < 25 \text{ mL/min/1.73 m}^2$.
- Pregnancy (see [Section 7.6.1.1](#)).
- Any protocol deviation (including prohibited concomitant therapy, see [Section 6.9.3](#)) that results in a significant risk to the patient's safety or that will interfere with the assessment of the efficacy endpoints of this trial, including significant non-compliance with the trial protocol and procedures.

In addition to the general treatment discontinuation criteria, the toxicity-related criteria listed below will also require IMP treatment discontinuation. The final decision to discontinue IMP treatment is up to the judgment of the Investigator.

Hepatic-related Discontinuation Criteria

- ALT or AST levels $> 8 \times$ upper limit of normal.

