- e Historical kidney volume will be collected, if available in medical records, in patients with confirmed ADPKD.
- f Serum pregnancy test at screening; urine pregnancy test at other visits.
- g Pre-dose.
- h Performed within 4 weeks prior to the Day 1 Visit.
- i Pre-dose and 24 ± 4 hours after dose.
- j Pre-dose and 24 ± 14 hours after dose.
- k Triplicate 12-lead ECG will be performed.

	Screening	Double-Blind Treatment Period ^a							
		D1	D8	D29	D85	D141	D169	D267	D365
Procedure/Assessment	W-12 to -1	W1	W2 ^b	W5	W13	W21	W25	W39	W53 ^c
Gallbladder examination ^l	X ^{m,n}								
MRI of liver and kidney volume and total liver cyst volume	X ^{h,o}				X ^p		X ^p		X ^p
Administration of IMP ^q		X	X	X	X	X	X	X	X
eGFR sampling (creatinine, cystatin C)	X	X ^g			X ^g		X ^g		X ^g
Plasma samples for octreotide measurement		X ^g			X ^r		X ^j	X ^g	X ^g
Immunogenicity		X ^g			X ^g		X ^g		X ^g
PLD-S	X	X ^g			X ^g	X ^g	X ^g	X ^g	X ^g
PLD-I	X	X ^g			X ^g	X ^g	X ^g	X ^g	X ^g
PGI-S	X	X ^g			X ^g	X ^g	X ^g	X ^g	X ^g
PGI-C					X ^g	X ^g	X ^g	X ^g	X ^g
SF-36		X ^g					X ^g		X ^g
PLD-Q		X ^g					X ^g		X ^g

- ^l Gallbladder imaging may be repeated during the trial if symptoms of cholelithiasis appear (ultrasound is first choice).
- ^m Historical gallbladder imaging assessments performed within 4 months before Day 1 Visit, may be used as baseline measurement. If such a gallbladder ultrasound or MRI is available and includes satisfactory information on presence of gallstones, gallbladder sludge or other findings, the screening gallbladder ultrasound does not need to be performed.
- ⁿ If the MRI of the liver and kidneys performed at screening, Week 77, Week 125 and Week 173/End-of-Treatment include satisfactory images of the gallbladder, these scans may also be used for the safety assessment by the Investigator.
- ^o The eligibility htTLV value will be calculated according to local clinical practice either using the MRI at screening or based on available historical imaging, as long as that the latter fulfils the imaging and schedule requirements of the trial (see footnote ^h and Section 7.3.1).
- ^p Visit window ± 3 days.

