4.6 Pharmacokinetic Analysis Set

The PK analysis set comprises all patients who were administered at least 1 dose of CAM2029 and for whom at least 1 plasma octreotide concentration after the first CAM2029 dose is available.

The PK analysis set will be used for the analyses of PK data.

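### As visible, SAP 5.11 summarises octreotide by regimen at each visit without requiring recent dosing, so off-drug samples can lower the means and may mimic a decline to Week 53

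*SAP*

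**What the plan says.** SAP 4.6 gives the definition: "The PK analysis set comprises all patients who were administered at least 1 dose of CAM2029". At least one later octreotide result must also exist. Protocol 8.6.4 is equivalent. Neither has a condition on current or recent dosing.

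SAP 5.11 applies the set: "The PK analysis set will be used for all summaries of plasma octreotide concentrations in this section unless specified otherwise". On the level of summary it says that "octreotide concentration will be presented at each scheduled time point by CAM2029 dose regime". Protocol 8.12 follows the same plan. SAP 5.11 also lists every concentration and plots individual profiles.

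Off-drug samples are part of the design. Protocol 4.1.2 says that patients who discontinue IMP in the double-blind period "will continue to be followed in the trial and complete all the assessments up to Week 53", and Protocol 6.10.1 repeats it: "They should return for the assessments indicated in Table 3, up to Week 53". The Table 3 row "Plasma samples for octreotide measurement" has entries at Day 1 and Weeks 13, 25, 39 and 53. Week 13 is a full profile, Week 25 adds a sample around 24 hours, and Weeks 39 and 53 are pre-dose only. Both protocol sections also ask for a PK sample at least 5 weeks after the last dose. Protocol 6.2.2 says that missed doses are not made up and that "the patient will continue treatment with the next scheduled dose as planned regardless of how many doses they miss".

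Values below the limit of quantification count as 0 in SAP 5.11 but as the limit itself in SAP 5.3.4.

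**The concern.** The secondary PK objective concerns octreotide after CAM2029 administration, and the tables are labelled by dose regimen. A reader will take a Q1W or Q2W mean as exposure on that regimen. A patient months off drug who still attends does not describe it, yet under the visible rule that patient's sample enters the mean.

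Stopping accumulates, so any such dilution is larger at Week 53 than at Week 13. A falling pre-dose mean could be misread as loss of exposure or, next to the immunogenicity tables, as antibody-driven clearance. Unequal stopping between the arms would distort the descriptive comparison of Q1W with Q2W.

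The SAP limits other data to the treated period. SAP 5.10.1 ends treatment-emergent events no later than last dose plus five half-lives, and SAP 5.10.2 counts the worst CTCAE laboratory grade only while on IMP. Concentration, the variable most directly tied to dosing, has no visible counterpart.

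**Working it through.** **Inputs.** Half-life 10.6 days (SAP 5.10.1); five half-lives given as 53 days (SAP 5.8.1). Week 13 and Week 53 fall on Days 85 and 365 (Protocol Table 3), i.e. 84 and 364 days after Day 1. Arm size 69/3 = 23. The share of an arm that stops IMP and still attends is not in the documents; it is assumed at 5% to 30%.

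**Plan's own figure.** 5 × 10.6 = 53.0 days. It reproduces.

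**Residual drug after stopping.** Assuming mono-exponential decline, the fraction of trough left d days after the next dose was due is 2^(−d/10.6): 40% at 14 days, 16% at 28, 10% at 35, 3.1% at 53 and 0.4% at 84.

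**Is there a trend without stoppers?** By Week 13 pre-dose, 1 − 2^(−84/10.6) = 99.6% of steady state is reached. Arm 2 starts on active drug (Protocol 6.5.2), so its active doses fall in odd weeks, and the pre-dose samples at Weeks 13, 25, 39 and 53 all come 14 days after the last active dose. Neither accumulation nor the alternation with placebo creates a decline.

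**Dilution by stoppers.** Set the on-treatment trough to 1 and flat. Let a share D stop evenly over 364 days, all still attending. With k = ln 2/10.6 = 0.0654 per day, the mean t days after Day 1 is

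M(t) = 1 − D × (t/364) × [1 − (1 − e^(−kt))/(kt)].

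For D = 15%: M(84) = 1 − 0.0346 × (1 − 0.181) = 0.972; M(364) = 1 − 0.15 × (1 − 0.042) = 0.856; ratio 0.881.

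| D (assumed) | Week 13 | Week 25 | Week 39 | Week 53 | Week 53/Week 13 |
|---|---|---|---|---|---|
| 5% | 0.991 | 0.979 | 0.966 | 0.952 | 0.961 |
| 10% | 0.981 | 0.958 | 0.931 | 0.904 | 0.922 |
| 15% | 0.972 | 0.937 | 0.897 | 0.856 | 0.881 |
| 20% | 0.962 | 0.916 | 0.862 | 0.808 | 0.840 |
| 30% | 0.943 | 0.874 | 0.793 | 0.713 | 0.755 |

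With no stoppers, or only stoppers well before Week 13, the ratio is 1.00. In an arm of 23, each later stopper with negligible residual drug lowers the Week 53 arithmetic mean by 1/23 = 4.3%; three lower it by 13%.

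**Spread.** If a share p is near zero and the on-drug CV is c, the reported CV is √[(1 + c²)/(1 − p) − 1]. With c = 50% (assumed), it is 56%, 69% and 89% for p = 5%, 15% and 30%.

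**Skipped doses.** One active dose missed just before a visit leaves 2^(−7/10.6) = 63% of the expected trough on Q1W and 2^(−14/10.6) = 40% on Q2W. This can precede any visit.

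**Below-quantification rule.** The limit is redacted, so take it as 1% to 10% of trough (assumed). With 3 of 23 patients set to the limit, the geometric mean is multiplied by 0.01^(3/23) = 0.55 to 0.1^(3/23) = 0.74. With those values set to 0, the geometric mean is zero or undefined.

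**The case against.** The strongest reply is that no one knows whether the problem will occur. A reader might infer that the plan will necessarily show a false fall from Week 13 to Week 53. The documents do not support that: it needs patients who stop after Week 13 and still attend, and no such number is given. Nor can the 15% in Protocol 8.2 and SAP 6 supply it. That is a drop-out allowance for sample size, and a patient who has left gives no Week 53 sample. It is equally tempting to blame skipped doses for a trend, but they can affect any visit. All of this stands, and the point is worded conditionally for that reason.

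Second, the text is incomplete. Part of SAP 5.11 is not shown, SAP 5.2.3 and 5.15 appear as headings only, the appendices are absent, and the analysis-set sentence allows exceptions. A rule may exist out of sight. This lowers certainty, but nothing visible points to one.

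Third, the listings, individual profiles, count of non-zero values, minimum and maximum would reveal off-drug values, antibody data are available for cross-checking, and no formal Week 13 versus Week 53 test is planned. That limits the harm but does not correct the means.

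Fourth, the mean over all attenders is a legitimate description of that group, and restricting to adherent patients selects on a post-randomisation event: if high-exposure patients stop for intolerance, that too creates a trend. This is a fair reason to show both tables.

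**Conclusion.** The point holds in conditional form. On the visible text, by-visit regimen summaries include every PK-set patient sampled at that visit, whatever their recent dosing, while the protocol keeps collecting samples from patients who have stopped. Means can be too low and spread too wide as descriptions of on-treatment exposure.

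An apparent decline in the pre-dose samples arises only if patients stop after Week 13 and still attend. The fall in the arithmetic mean is then 3.9% to 24.5% (ratios 0.961 to 0.755) for 5% to 30% of an arm, assuming even stopping, full attendance, mono-exponential decline and flat on-treatment exposure. The geometric mean is more sensitive and depends on which below-quantification rule is used. Only pre-dose samples bear on this, since Week 53 has no others.

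The consequence is confined to descriptive secondary PK results. The primary endpoint, alpha and power are untouched. It is worth correcting before unblinding, because excluding low values afterwards would look post hoc.

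**What to change.** If a sample-handling rule already exists in text not shown, cite it in SAP 5.11. Otherwise add there:

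- An evaluable-sample flag: the regimen's active doses were taken as scheduled over a stated run-in before the sample, and the sample lies within its window. The latest dose alone is not enough. With r = 0.633 per week, a Q1W patient who took the last dose but missed the one before is at 1 − r(1 − r) = 77% of the steady-state trough. Five half-lives (53 days), the SAP's own yardstick, is one option for the run-in; a shorter one keeps more samples.
- By-regimen summaries and mean profiles on flagged samples, with all other concentrations listed.
- Post-discontinuation samples summarised by time since last CAM2029 dose.
- The all-samples table kept as a supplement.
- One rule for values below quantification, replacing the conflicting statements in SAP 5.11 and 5.3.4.

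The cost is SAP wording and one derived variable. Exact dose and sample times are already required in the eCRF (Protocol 6.2.1 and 7.4.1). The downside is slightly fewer values per time point and selection on adherence, which the supplementary table makes visible.

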5.12 Pharmacodynamic Analyses

5.13 Immunogenicity Analyses

Blood samples for immunogenicity assessment of ADA will be taken according to the protocol Table 3.

ADA status (e.g. positive, negative) will be summarized by frequency counts and percentages at each assessment time point. In addition, number and percentages of patients with positive ADA responses at any post-baseline assessments will be summarized. Titer values will be summarized descriptively.

If presence of ADA, the neutralizing capacity of the antibodies (NAb) will be analyzed and presented in listings.

All immunogenicity results will be present in a data listing.

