4.2.2 Selection of Endpoints

The primary endpoint in this trial is change in htTLV from baseline to Week 53 assessed by MRI volumetry. Assessment of TLV or htTLV has been used as primary outcome measure in PLD trials since established molecular biomarkers for detection and monitoring of PLD are lacking. Liver volume has been associated with both symptom severity, and quality of life (18).

To assess the PLD-related symptom burden and the impact of disease on functioning and well-being from the patient perspective, two PLD-specific PRO instruments, PLD-S and PLD-I, are currently under development (see Sections 7.3.3.1 and 7.3.3.2). These are included as secondary outcomes to assess treatment effect on patient reported PLD-related symptoms and impact on functioning and well-being, together with evaluation of the effect on liver volume, liver cyst volume and kidney volume (in patients with kidney cysts) over time, health-related quality of life, safety, tolerability and plasma concentrations of octreotide. Treatment effect on renal function in patients with presence of kidney cysts is also included as a secondary endpoint.

[REDACTED]

In addition, the immunogenicity of CAM2029 will be assessed due to the immunogenic potential of octreotide (36).

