5.3 Exclusion Criteria

Patients meeting any of the following criteria will not be eligible to participate in the clinical trial:

1. Surgical intervention for PLD within 3 months before screening. *For sclerotherapy patients, at least 6 months before screening.*
2. Treatment with an SSA within 3 months before screening.
3. Non-responsive to previous treatment of PLD with an SSA as per the Investigator's assessment.
4. Symptomatic cholelithiasis within 3 months before screening or previous medical history of cholelithiasis induced by SSAs unless treated with cholecystectomy.
5. Presence of extrahepatic cysts that, in the Investigator's opinion, may prevent the patient from safely participating in the trial.
6. Severe kidney disease, as defined by $\text{eGFR} < 30 \text{ mL/min/1.73 m}^2$.
7. Severe liver disease defined as liver cirrhosis of Child-Pugh class C.
8. Use of oral estrogen contraceptives or supplementation within 3 months before screening.
9. Poorly controlled diabetes (hemoglobin A1c $\geq 10\%$) at screening.
10. Patients with a known history of hypothyroidism, unless they have been on adequate and stable replacement thyroid hormone therapy for at least 3 months before the first dose of the IMP.
11. Uncontrolled hypertension defined by a systolic blood pressure of $> 160 \text{ mmHg}$ and/or diastolic blood pressure of $> 100 \text{ mmHg}$ at screening.

12. History of significant cardiac disease or current diagnosis of cardiac disease indicating significant risk of safety for patients participating in the trial, such as uncontrolled or significant cardiac disease, including any of the following:
 - a. History of myocardial infarction, angina pectoris or coronary artery bypass graft within 6 months before screening.
 - b. Clinically significant cardiac arrhythmias (e.g., ventricular tachycardia), complete left bundle branch block or high-grade atrioventricular block (e.g., bifascicular block, Mobitz type II and third-degree atrioventricular block).
 - c. Long QT syndrome, family history of idiopathic sudden death or congenital long QT syndrome, or any of the following:
 - i. Risk factors for Torsades de Pointes including uncorrected hypokalemia or hypomagnesemia, history of cardiac failure or history of clinically significant/symptomatic bradycardia.

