2.2 Trial Design

This is a Phase 2/3 (Phase 2b in the US), randomized, placebo-controlled, double-blind, multi-center trial designed to evaluate the efficacy and safety of 2 treatment regimens of CAM2029 versus placebo in patients with PLD. Approximately 69 patients will be randomized in the trial.

The trial consists of an up to 12-week Screening Period followed by a 52-week (12-month) Double-Blind Treatment Period for which patients will be randomized in a 1:1:1 ratio to 1 of the 3 treatment arms:

- Arm 1: CAM2029 10 mg once weekly
- Arm 2: CAM2029 10 mg every 2 weeks (weekly alternation with placebo)
- Arm 3: Placebo once weekly

Following completion of the Double-Blind Treatment Period, all patients will continue to a 120-week (30-month), open-label, single-arm, extension period with CAM2029 10 mg once weekly, followed by an 8-week safety follow-up period. The estimated duration of the trial for each patient is approximately 47 months.

A primary endpoint analysis will be performed when the last patient has completed the Double-Blind Treatment Period (Week 53).

An overview of the trial design is shown in [Figure 1](#).

[figure not shown]

Figure 1: Trial design

CL: clinical laboratory sampling; FU: follow-up; MRI: magnetic resonance imaging; N: number of patients; R: randomization

a Dose reduction to CAM2029 10 mg every 2 weeks will be allowed in the Extension Period.

The trial population is comprised of adult patients (≥ 18 years) who are diagnosed with PLD associated with ADPKD or isolated as in ADPLD, and who meet all the inclusion criteria and none of the exclusion criteria specified in Section 5 of the clinical trial protocol.

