5.2 Time Points and Visit Windows

5.2.1 Definition of Baseline

Baseline is defined as the last available observed value of the parameter of interest prior to the first administration of IMP during the double-blind treatment period (this includes unscheduled visits). For 12-lead ECG, baseline is defined as the average of the last non-missing triplicate measurements prior to the first administration of IMP. If there are less than 3 measurements, the available measurements will be used.

Change from baseline is calculated as post-baseline value minus the baseline value.

[figure not shown]
Percentage change from baseline is calculated as follows: $(\text{post-baseline result} - \text{baseline result}) / \text{baseline result} * 100$.

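### The only cumulative ADA summary ignores the Day 1 result, so a patient in any arm who is antibody-positive before dosing and stays positive would be counted as a responder

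*SAP*

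**What the plan says.** Protocol 4.2.2 gives the purpose: "the immunogenicity of CAM2029 will be assessed due to the immunogenic potential of octreotide". The question is therefore what CAM2029 does to antibody status.

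SAP 5.13 plans the following:

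- By visit: "ADA status (e.g. positive, negative) will be summarized by frequency counts and percentages at each assessment time point".
- Cumulatively: the "number and percentages of patients with positive ADA responses at any post-baseline assessments will be summarized".
- Titres: "Titer values will be summarized descriptively".
- Neutralizing antibody results in listings, and a listing of all immunogenicity results.

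Protocol Table 3 schedules double-blind immunogenicity samples before dosing on Day 1 and at Weeks 13, 25 and 53. SAP 5.2.1 makes the Day 1 sample the baseline: "Baseline is defined as the last available observed value of the parameter of interest prior to the first administration of IMP".

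On earlier exposure, Protocol 5.3 excludes "Treatment with an SSA within 3 months before screening" and patients whom the investigator judges non-responsive to an earlier SSA given for PLD. No eligibility criterion refers to ADA status.

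Neither document defines treatment-induced, treatment-boosted or treatment-emergent ADA. Protocol 7.6.4 covers sampling only, and Protocol section 8 contains no immunogenicity analysis.

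**The concern.** A post-baseline positive can arise in three ways: the antibody appeared on treatment, it was present before treatment and rose, or it was present before treatment and did not change. Only the first two bear on the immunogenicity of CAM2029. The cumulative count in SAP 5.13 adds all three together.

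A Day 1 positive is plausible here. Protocol 2.1.1 says that somatostatin receptor ligands are used off-label for symptomatic PLD, and the eligibility rules admit patients treated earlier. The protocol's reason for testing, that octreotide can provoke antibodies, applies equally to octreotide given before the trial. A non-specific assay result is another possible source.

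The stake is how one descriptive safety figure is read. In arms of about 23, one or two patients who were positive before dosing would visibly move the percentage, and a chance imbalance between arms could be mistaken for a difference in immunogenicity or hide one. A real boost in a patient positive on Day 1 would not stand out either, because titres are summarized without any criterion for a rise over baseline.

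**Working it through.** The plan states no ADA figure, so there is nothing to reproduce. The check is a reading of the rule followed by an illustration.

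**Reading.** Take a patient positive on Day 1 and positive again at Week 13 with an unchanged titre.

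- The by-visit table counts this patient once under Day 1 and once under Week 13. These are separate marginal counts and do not show that it is the same person.
- The cumulative count includes the patient, because the only condition is positivity at a post-baseline sample.
- The titre summary gives descriptive statistics and does not classify the patient as unchanged.

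The SAP does relate outcomes to baseline elsewhere. SAP 5.10.1 restricts treatment-emergent adverse events to those that began or got worse after the first dose. SAP 5.10.2 tabulates the worst post-baseline laboratory grade without regard to baseline, but pairs it with a shift table. ADA has neither device.

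**Inputs for the illustration.**

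- SAP 2.2: "Approximately 69 patients will be randomized in the trial", allocated 1:1:1. That is 69 / 3 = 23 per arm, and 46 on CAM2029.
- b, the share positive on Day 1: not in the documents; assumed 2%, 5% or 10%.
- p, the share of those still positive later: not in the documents; set to 1, which gives an upper bound.
- Every patient gives a post-baseline sample: assumed.

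**Expected patients counted without any induction** = n × b × p, with p = 1:

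| b | Per arm (n = 23) | Both CAM2029 arms (n = 46) | Chance that an arm of 23 has at least one Day 1 positive, 1 − (1 − b)^23 |
|---|---|---|---|
| 0% | 0 | 0 | 0% |
| 2% | 0.46 | 0.92 | 37% |
| 5% | 1.15 | 2.3 | 69% |
| 10% | 2.3 | 4.6 | 91% |

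The last column is the chance that an arm contains a Day 1 positive. It is not the chance that the reported rate is inflated, which also needs persistence. If only half persisted (p = 0.5), the expected counts would halve.

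**Weight of one patient:** 1/23 = 4.3 percentage points of an arm, or 1/46 = 2.2 points of the combined CAM2029 group.

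**With some true induction.** Let i be the induction rate among Day 1 negatives. The rule as written gives b + (1 − b) × i. For b = 5% and i = 5%, this is 0.05 + 0.95 × 0.05 = 9.75%, or about 4.5 of 46. The treatment-induced count is 46 × 0.95 × 0.05 = 2.2, which is 5.0% of the 43.7 Day 1 negatives (46 × 0.95) or 4.75% of all 46.

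**The case against.** The best defence is that the information is not lost. Day 1 positives have their own line in the by-visit table, all results are listed, and with about 23 patients per arm a reader can trace each one by hand. This stands, and it limits the point to one missing cross-classification. It does not remove the point: no planned summary does the tracing, and a definition of induced or boosted made at that stage would be made after unblinding.

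The placebo arm is a second defence. The rule is the same in every arm, so the placebo percentage shows the background of pre-existing and non-specific positives. This stands in part. About 23 patients estimate a low background rate poorly, and chance imbalance remains.

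Third, the table shells are a separate document, assay methods are provided separately, and the SAP appendices are not visible. A baseline column or a treatment-emergent line could exist there. That cannot be excluded, but SAP 5.13 refers to neither the shells nor the appendices for a definition.

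A reader might infer that pre-existing antibodies will inflate the CAM2029 arms in particular, or that the trial's main immunogenicity conclusion will be wrong. The documents support neither inference. The rule covers placebo equally. Any inflation depends on a Day 1 prevalence and a persistence that the documents do not give. SAP 5.13 plans no ADA hypothesis test, safety parameters are descriptive (SAP 5.1), and nothing presents this count as a headline result.

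**Conclusion.** The point holds as a minor, conditional one. As written, the cumulative ADA summary cannot distinguish antibodies that treatment induced or boosted from those present beforehand and unchanged, in any arm, although the sample needed to do so is scheduled.

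The size is known only under assumption. For Day 1 prevalences of 2%, 5% or 10%, the upper bound is an expected 0.5, 1.2 or 2.3 patients per arm of 23, at 4.3 percentage points each. This assumes that every Day 1 positive stays positive and that all patients are followed up. At zero prevalence, the rule as written and a treatment-induced count agree. The primary and key secondary analyses are not affected.

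**What to change.** In SAP 5.13, make the cumulative summary treatment-emergent ADA, by arm including placebo, with two components:

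- Treatment-induced: negative on Day 1 and positive at any later double-blind sample.
- Treatment-boosted: positive on Day 1, with a later titre rise above a factor fixed from the assay validation before unblinding.

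Show two further groups on their own lines: patients positive on Day 1 without such a rise, and patients with no Day 1 result. The second group should not be treated as negative, since an unmeasured pre-existing antibody would then count as induced.

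State the denominator as patients with at least one post-baseline ADA result. SAP 5.13 names no analysis set, and SAP 5.1 otherwise defaults to the whole set.

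The cost is SAP wording, one derived variable and a titre factor that the documents do not yet supply, which must be fixed before database lock. No new samples are needed. SAP section 2 allows changes until database lock and unblinding for the primary analysis.
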